Rapid Administration of Carnitine in sEpsis (RACE)

NCT01665092

May 15, 2019

Study Protocol

This study was a prospective, randomized, blinded, placebo-controlled, clinical trial utilizing Bayesian response-adaptive randomization, and designed to assess the efficacy of L-carnitine to decrease the sequential organ failure assessment (SOFA) score of patients with septic shock. SOFA score is an organ failure scoring system consisting of 6 physiological systems that ranges from 0-24, and a score of 2 or more is required for the diagnosis of sepsis. The trial took place from January 2013 to February 2018 in the emergency departments and intensive care units of sixteen large urban medical centers in the United States. The research protocol was approved by the local institutional review boards and performed in accordance with Good Clinical Practice guidelines.

Participants

Patients presenting to the participating centers during the study period with septic shock were assessed for inclusion. Criteria for inclusion were patients of age ≥ 18 years with confirmed or presumed infection, the presence of two or more systemic inflammatory response criteria, enrollment within 24 hours of recognition of septic shock with initiation of a standardized sepsis treatment pathway, high dose vasopressors (norepinephrine > 0.05 mcg/kg/min; dopamine > 10 mcg/kg/min; phenylephrine > 0.4 mcg/kg/min; epinephrine > 0.05 mcg/kg/min; or any vasopressin dose) to treat shock for ≥ 4 hours at the time of enrollment, cumulative sequential organ failure assessment (SOFA) score of ≥ 6 , and blood lactate level > 2.0 mmol/L. Patients were excluded if they were pregnant or breastfeeding, had any primary diagnosis other than sepsis, had an established do not resuscitate status or advanced directive restricting aggressive care, any history of seizures, known inborn error of metabolism, anticipated surgery that would interfere with the 12 hour infusion, active participation in another interventional trial, cardiopulmonary resuscitation prior to enrollment, known allergy to L-carnitine, severe immunocompromised state (absolute neutrophil count $< 500/\mu\text{L}$), or active warfarin treatment.

Eligible patients were screened 7 days per week using electronic medical record based reports of admitted patients receiving both antibiotics and vasopressors and/or pager-based alerts informing study staff regarding the initiation of a sepsis treatment pathway (which comprised the screening log), in addition to active screening of the emergency department tracking board to facilitate earlier identification. Each enrolled patient, or the patient's legally authorized representative (LAR), provided written informed consent prior to randomization and collection of data.

Treatment Assignment

After informed consent was obtained, a centralized web-based portal was used to determine treatment allocation. Patients were randomly assigned to one of three doses of L-carnitine or saline placebo. During an initial "burn in" period of 40 patients, participants were allocated equally among the treatment arms. From that point on, interim analyses were conducted every 12 patients. At each interim analysis the relative allocation probability of the three active arms were adjusted to be proportional to the probability each arm would lead to the greatest improvement in SOFA score. A site-based blocked randomization approach ensured that approximately one-third of participants were allocated to the control arm throughout the trial to maintain a sufficient allocation to control and to avoid confounding

from local changes in usual care. Predefined stopping rules for both efficacy and futility were determined prior to trial initiation. The statistical rationale and methodology has been published previously.

Treatment Interventions

The three treatment arms consisted of low (6 grams), medium (12 grams), and high (18 grams) doses of L-carnitine administered intravenously over a 12-hour period. The control (placebo) consisted of an identical volume of 0.9% saline placebo. Following randomization, research pharmacists used a web-based portal to determine treatment allocation. Pharmacists were the only individuals not blinded to treatment, and had no study-related contact with the investigators or participants. Pharmacists and staff prepared either L-carnitine or placebo in identical polypropylene infusion bags with labels including the study ID number, patient name, medical record number, and infusion rate. For each dose of L-carnitine, 33% of the total dose was administered as a 20 mL bolus over 2-3 minutes followed by a fixed rate continuous infusion of 1 L over the next 12 hours. The study solution was administered through intravenous catheters using FDA-approved medical equipment (IV tubing, IV pumps, etc). Levocarnitine was provided by Leadiant Biosciences (Gaithersburg, MD, United States; formerly Sigma Tau Pharmaceuticals) and maintained by pharmacy staff, with tracking of lot numbers of L-carnitine administered. For safety, clinical physicians could elect to break study blinding, though in no instance did this occur.

Assessments and Outcome Measures

During the study treatment period the patient's physiologic parameters, laboratory results, and medical treatments were recorded. Sex, race, and ethnicity were self-reported. An investigator performed a bedside assessment and recorded vital signs, vasopressor requirements, ventilator settings, and Glasgow Coma Scale at enrollment, 12, 24 and 48 hours later. At enrollment and 48 hours blood samples were sent to the clinical laboratory for platelet count, creatinine, and total bilirubin to ensure capture of SOFA score parameters. Non-protocol (clinical) laboratory results obtained between 0 and 48 hours were recorded. Patients were followed until hospital discharge or death and then up to one year using the patient's electronic medical record and phone calls to the patient or LAR, cross-referenced with the social security death index. Study data were collected and managed using REDCap.

The primary endpoints were change in SOFA score from enrollment to 48 hours, with negative numbers indicating improvement, and 28-day mortality. In the event of early death prior to 48-hours, last-value carried forward was utilized. Secondary outcomes included ICU and hospital length of stay and percentage of patients undergoing withdrawal of care. Three preplanned blinded interim safety analyses were performed: after a burn-in phase of 40 patients, and then after one-third and two-thirds of participants were enrolled. The unblinded results were reviewed by an independent Data Safety Monitoring Board with the authority to terminate the study for safety concerns or if the predefined stopping rules for efficacy or futility were fulfilled. The trial was registered on clinicaltrials.gov (NCT01665092) prior to initiation and this report was designed to conform to the recommendations of the CONSORT statement.

Statistical Analysis

The trial was considered positive if 1) the posterior probability of any dose decreasing the SOFA more than placebo exceeded 90%, and 2) given (1), there was at least a 30% predictive probability that the most promising dose would be successful in reducing 28-day mortality in a subsequent two arm, 2,000 total patient phase III trial. Based on Monte-Carlo simulation of 30,000 simulated trials enrolling up to 250 patients, the probability of a positive trial assuming no treatment effect (the type I error rate α) was 4.3%. The power of the trial (β) was dependent on the true treatment effect. If the true SOFA effects for the three L-carnitine arms were 0, 1 and 2, corresponding to mortality effects of 0, 6%, and 12%, then the power of the trial was 91.1%.

Changes in SOFA scores between groups were analyzed using a Bayesian approach, assuming a normal dynamic linear model dose response, and posterior probabilities are reported. The normal dynamic linear model is a Bayesian analogue to a smoothing spline whose smoothness is determined by a tuning parameter. The tuning parameter is given a prior and thus is determined by a combination of the prior and the observed data. The prior was selected during the design process to provide a smooth fit while maintaining the main features of the observed data.

Conditional on a declaration of SOFA reduction, predictive probabilities of success in a subsequent phase III trial were calculated using non-informative priors. Except for these primary outcomes, remaining data were analyzed using frequentist statistics. Categorical data were compared using Chi-square tests, while continuous variables were compared with ANOVA or Wilcoxon rank sum based on normality. All non-Bayesian tests were 2-sided with $p < 0.05$ considered significant. All trial design simulations, interim analyses, and Bayesian statistics were performed using the Fixed and Adaptive Clinical Trial Simulator Software (FACTS, Berry Consultants, LLC; Austin, TX, United States), while frequentist statistics were conducted using STATA 15.1 (StataCorp LLC, College Station, TX). [name] and [name] had full access to all the data in the study and take responsibility for the integrity of the data and the accuracy of the data analysis.

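### Deaths before 48 hours are carried forward with no death-ranked check, so the SOFA endpoint behind criterion 1 and active-arm allocation can largely miss them

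*Combined protocol and SAP*

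**What the plan says.** The combined protocol and SAP has two primary endpoints: SOFA change from enrollment to 48 hours, and 28-day mortality. The only rule for death inside the 48-hour window is in Assessments and Outcome Measures: "In the event of early death prior to 48-hours, last-value carried forward was utilized".

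That SOFA change is used twice:

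- **Allocation.** Under Treatment Assignment, after a burn-in of 40 patients and then every 12 patients, the active-arm probabilities were "adjusted to be proportional to the probability each arm would lead to the greatest improvement in SOFA score".
- **Criterion 1.** Under Statistical Analysis, a positive trial first requires that "the posterior probability of any dose decreasing the SOFA more than placebo exceeded 90" percent.

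Mortality enters the success rule second. Criterion 2 requires that "there was at least a 30% predictive probability that the most promising dose would be successful in reducing 28-day mortality" in a later 2,000-patient trial, and the order is explicit: "Conditional on a declaration of SOFA reduction, predictive probabilities of success in a subsequent phase III trial were calculated".

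On what could be carried, bedside staff "recorded vital signs, vasopressor requirements, ventilator settings, and Glasgow Coma Scale at enrollment, 12, 24 and 48 hours later". The laboratory components were scheduled less often: "At enrollment and 48 hours blood samples were sent to the clinical laboratory for platelet count, creatinine, and total bilirubin". Clinical laboratory results from the 48-hour window were also kept. The documents do not say how a last value is put together from components measured at different times. Treatment Assignment refers to an earlier methods publication, which may define it but is not available here.

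**The concern.** Carry-forward scores a death as the last reading before it. If the patient died before much deterioration was recorded, the score is close to no change, which is only a little worse than the improvement expected in an average survivor. If the patients who die are those whose SOFA would have risen most, carry-forward replaces a bad 48-hour value with a milder one, and extra deaths improve the arm's mean.

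Two errors follow. An arm with more early deaths may lose little or nothing on criterion 1 and in allocation. An arm that prevents early deaths may get little credit, and if it fails criterion 1 it cannot support a positive declaration, because the mortality prediction is made only after a SOFA reduction is declared. Entry requires septic shock on vasopressors, SOFA of at least 6 and lactate above 2.0 mmol/L, so deaths within 48 hours are plausible, though their frequency is not given.

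**Working it through.** **The plan's own figures.** The stated power is 91.1% and type I error 4.3%, at up to 250 patients. The documents do not give the SOFA SD, control mortality, the prior or the stopping boundaries. A simulation of the adaptive design without early stopping gives power of 90.7% to 92.7% at an assumed SD of 4 (control mortality 30% to 50%), about 95% at SD 3 and 82% to 84% at SD 5. So SD 4 is a reasonable working value. Type I error came out at 5.8% to 9.8%; with those inputs missing, this does not show that 4.3% is wrong. Neither stated figure is tied in the documents to the death rule.

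**Inputs for the check.** From the documents: maximum 250 patients, control share about one-third (250/3 ≈ 83), criterion 1 threshold 90%. Assumed: natural 48-hour change normal with mean -2 and SD 4; early deaths 20% against 10%; no other treatment effect; carried change c (0 means the enrollment value); correlation ρ between the risk of early death and the natural 48-hour change.

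**Step 1: shift in the mean.** With death proportion p, mean m, SD s and φ(z_p) the normal density at the death cut-off:

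arm mean = m + p(c − m) − s·ρ·φ(z_p)

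φ is 0.2800 at p = 0.20 and 0.1755 at p = 0.10. The difference, excess-death arm minus the other, is

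0.1 × (c + 2) − 4 × (0.2800 − 0.1755) × ρ = 0.1 × (c + 2) − 0.418ρ

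- c = 0: 0.2 worse at ρ = 0, about 0 at ρ = 0.5, 0.2 better at ρ = 1. It crosses zero at ρ = 0.2/0.418 = 0.48.
- c = 0, means -1 to -3 and SD 3 to 5: from 0.3 worse (mean -3, ρ = 0) to 0.4 better (mean -1, SD 5, ρ = 1).
- c = 4 to 8: 0.6 to 1.0 worse at ρ = 0, and 0.2 to 0.6 worse at ρ = 1.

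**Step 2: chance of meeting criterion 1.** A two-arm stand-in was used: 83 per arm, flat prior, so the criterion becomes Z > 1.2816; 20,000 replicates per cell; uniform death times. The comparison rule ranks deaths below all survivors (earlier is lower) and analyses pooled normal scores.

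Hand check at ρ = 0, c = 0: the variances are 0.9 × 16 + 0.1 × 0.9 × 4 = 14.76 and 0.8 × 16 + 0.2 × 0.8 × 4 = 13.44. The standard error is √((14.76 + 13.44)/83) = 0.583, and 0.2/0.583 = 0.343. The excess-death arm passes with probability P(Z > 1.625) = 5%, and the arm with fewer deaths with P(Z > 0.939) = 17%.

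| Arm and setting | Carry-forward (ρ = 0, 0.5, 1) | Death ranked worst (ρ = 0, 0.5, 1) |
|---|---|---|
| No effect | 10% | 10% |
| 10 points more early deaths, c = 0 | 5%, 10%, 20% | 0.7%, 1.6%, 4.7% |
| 10 points fewer early deaths, c = 0 | 17%, 10%, 4% | 46%, 33%, 19% |
| 10% against 5%, excess arm, c = 0 | 8% to 18% | 3% to 8% |
| 10 points more early deaths, c = 4 | 1% to 6% | 1% to 5% |

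From about 6 carried points the two rules give similar rates. Independent re-runs agree within about 1 percentage point. Integer-rounded SOFA (5% to 20% against 1% to 5%) and arms of 56 and 83 (6% to 19% against 1% to 5%) change little.

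**Step 3: allocation.** A separate three-dose adaptive simulation (800 runs, flat priors, death scored 24 from an assumed baseline of 10) gave the high arm 10 points more early deaths and survivors 2 points better. Under carry-forward, criterion 1 was met in 82% of runs and that arm received 45% of patients; with death scored worst, 17% and 21%. The trial was positive in 14% of runs under carry-forward, against 11% with no difference between arms.

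The two-arm stand-in has no dose smoothing, stopping rules or adaptive allocation. Its figures compare two scoring rules; they are not the trial's operating characteristics.

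**The case against.** The base case is unkind to the plan. It carries the enrollment value for every early death, although bedside components were recorded at 12 and 24 hours; with uniform death times, 36/48 = 75% of early deaths would have a later assessment. At ρ = 1 and 20% deaths, those patients' natural mean change is -2 + 4 × 0.2800/0.20 = +3.6, so carrying 0 is hard to reconcile with any recording. This stands in part: if the 12- and 24-hour values lie on a straight line to each patient's 48-hour value, the 20% cell falls to 16% and the 18% cell to 15%. At ρ = 0 and 0.5 the rates are 6% and 11%, so those cells hardly move.

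Harm is actively favoured only when ρ exceeds about 0.48 and almost nothing is carried. That is true. Below it, though, early deaths still barely register, and benefit from preventing them goes largely uncredited. The scenario is also large: 10 points of mortality, all before 48 hours, against a largest design effect of 12 points at 28 days. The 10% against 5% case is smaller and points the same way.

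Mortality is handled directly as a primary endpoint, criterion 2 counts every death to 28 days, and there was an "independent Data Safety Monitoring Board with the authority to terminate the study for safety concerns". This does protect against a false positive declaration, as 14% against 11% in Step 3 shows. It does not correct allocation, and it cannot rescue a dose that fails criterion 1, although mortality would still be reported as a primary endpoint.

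The methods publication might define the last value or contain a death sensitivity analysis. What can be said is that these documents contain neither.

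**Conclusion.** The concern holds and should be fixed; confidence is medium. The plan states a scoring rule under which an excess or a reduction of deaths before 48 hours can leave criterion 1 and active-arm allocation almost unmoved. In the base case the rule lets an arm with 10 points more early deaths through criterion 1 roughly four to seven times as often as a death-ranked rule would (20/4.7 ≈ 4; 5/0.7 ≈ 7). It passes an arm with 10 points fewer early deaths well under half as often.

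These sizes rest on assumed early-death rates, mean change, SD, correlation and carried values. The real effect could be negligible if early deaths were few or balanced, or if about 6 or more points of worsening were carried. The documents do not allow that to be judged. The risk to the final declaration is limited by criterion 2; the risk to allocation and to detecting a benefit through fewer early deaths is not.

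**What to change.** Keep carry-forward as the prespecified primary analysis and add the following:

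1. State which SOFA components, at which times, form the last value.
2. Report, by arm, the number of deaths before 48 hours and the mean change carried for them. This shows directly whether carry-forward already registered those deaths.
3. Add one sensitivity analysis, labelled post hoc because enrollment ended in February 2018. Rank deaths before 48 hours below all survivors, with earlier death lower; rank survivors by SOFA change; enter the normal scores in the same dose-response model.
4. Qualify the SOFA conclusion if the two analyses disagree.
5. If the design is reused, evaluate a death-ranked allocation input by simulation before adopting it.

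**Cost.** A little analysis on existing data; patients were followed to discharge or death, so nothing new need be collected. Allocation already made cannot be changed, and ranked results are not in SOFA points.

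The ranked analysis also loses power when treatment does not affect early death. With 10% early deaths in both arms, power falls from 96–98% to 87–94% for a 2-point effect, and from 58–67% to 47–56% for a 1-point effect. With 5% early deaths the falls are from 96–98% to 93–96% and from 61–67% to 54–59%. At 10% early deaths, a real effect would pass carry-forward but fail the ranked check in 5–9% of trials (2 points) or 13–14% (1 point), and about 3% of trials would do so under no effect. For a 1-point effect that is about a fifth to a quarter of carry-forward passes (13/67 to 14/58). For this reason the ranked analysis should be a check on the primary analysis and not a replacement for it.

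### The primary SOFA model, as described, has no term for enrollment SOFA; adding one is a low-cost gain in precision, about 0–35% of variance on assumed inputs

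*Combined protocol and SAP*

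**What the plan says.** Under Assessments and Outcome Measures, "The primary endpoints were change in SOFA score from enrollment to 48 hours, with negative numbers indicating improvement, and 28-day mortality". Under Statistical Analysis, "Changes in SOFA scores between groups were analyzed using a Bayesian approach, assuming a normal dynamic linear model dose response". That section goes on to explain the smoothing (tuning) parameter and its prior. It mentions no covariate for this model or for any other analysis.

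Enrollment SOFA is in hand for everyone. Participants makes a "cumulative sequential organ failure assessment (SOFA) score of ≥ 6" an entry criterion. At enrollment and at 48 hours, "blood samples were sent to the clinical laboratory for platelet count, creatinine, and total bilirubin to ensure capture of SOFA score parameters". The endpoint itself cannot be computed without the enrollment value.

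Two further statements bear on the point. Treatment Assignment says that "The statistical rationale and methodology has been published previously", and that publication is not part of the documents. The opening section says that "The trial took place from January 2013 to February 2018", so the trial is complete.

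**The concern.** Analysing change from baseline is not the same as adjusting for baseline. It subtracts the enrollment score with a coefficient fixed at 1. If the true slope of 48-hour on enrollment SOFA is not 1, the change score carries baseline noise that a fitted slope would remove.

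The SOFA posterior is used twice: in the first success criterion (more than 90% probability that some dose beats placebo on SOFA) and in the allocation updates every 12 patients, through each dose's probability of being best. Avoidable noise makes both less precise. Under randomization it does not bias the dose contrasts on average.

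**Working it through.** **The plan's own figures.** The stated 91.1% power and 4.3% type I error cannot be reproduced by formula. The documents do not give the SD of SOFA change, control mortality, the values of the prior or the stopping thresholds. The simulation below is used only to compare the analysis with and without a baseline term.

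**Step 1: variance.** Let SD0 and SD48 be the SDs of SOFA at enrollment and 48 hours, k = SD48/SD0, and ρ their correlation.

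- Change score: SD0²(1 + k² − 2kρ)
- Baseline-adjusted: SD0²k²(1 − ρ²)
- Difference: SD0²(1 − kρ)², which is never negative and is zero only when the slope kρ equals 1

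The fraction saved is 1 − k²(1 − ρ²)/(1 + k² − 2kρ). For example, k = 1.25 and ρ = 0.5 gives 1 − (1.5625 × 0.75)/(2.5625 − 1.25) = 1 − 1.1719/1.3125 = 0.107. All values of k and ρ are assumed.

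| k | ρ=0.3 | 0.4 | 0.5 | 0.6 | 0.7 | 0.8 |
|---|---|---|---|---|---|---|
| 1.0 | 35% | 30% | 25% | 20% | 15% | 10% |
| 1.25 | 22% | 16% | 11% | 6% | 2% | 0% |
| 1.5 | 13% | 8% | 4% | 1% | 0% | 5% |

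The entry floor narrows the enrollment distribution and so tends to push k above 1. For example, take normal scores with enrollment mean 9, SD 3.5, ρ = 0.6 and k = 1 before the cut at 6. After the cut, k is 1.205, ρ is 0.497 and the saving is 13%. Other illustrative truncated cases gave savings from about 1% to 24%.

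**Step 2: chance of a positive trial.** The simulation used 8,000 trials per setting, 250 patients, a burn-in of 10 per arm, updates every 12, one-third on control, and doses allocated by their probability of being best. The first criterion was a largest posterior above 0.90. The second was a predictive probability of at least 0.30 with 1,000 per arm, using Beta(1,1) priors and a two-sided 0.05 test. SOFA effects were 0/1/2 and mortality effects 0/6/12%, as in the plan; control mortality of 40% is assumed. Arms were modelled independently with flat priors, without the smoothing model or early stopping.

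| SD of change | Unadjusted | Gain at 4% saved (k=1.5, ρ=0.5) | 11% (1.25, 0.5) | 20% (1, 0.6) | 35% (1, 0.3) |
|---|---|---|---|---|---|
| 3 | 0.947 | 0.002 | 0.002 | 0.005 | 0.008 |
| 4 | 0.911 | 0.006 | 0.014 | 0.021 | 0.030 |
| 5 | 0.840 | 0.003 | 0.020 | 0.039 | 0.068 |

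The Monte Carlo SE of a difference is about 0.004–0.006, so the gains of 0.006 or less cannot be told from zero. Under no effect, the rate of positive trials was 0.091 unadjusted and 0.089 adjusted. Because 0.091 is not the plan's 4.3%, the 0.911 at SD 4 does not reproduce the plan's power; only the differences are used.

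**Step 3: chance imbalance.** For 83 control and 84 dose patients (83 is about one-third of 250; 84 is an assumed illustration), SE = SD0 × √(1/83 + 1/84) = 0.155 × SD0. This is 0.46 points at SD0 = 3 and 0.62 at SD0 = 4. The probability of a baseline difference of 1 point or more is 2Φ(−1/SE), or 0.031 and 0.106. The unadjusted contrast retains a share (1 − kρ) of any imbalance. A 1-SE imbalance therefore shifts it by about 0 to 0.4 points for ρ of 0.4–0.7 and k of 1.0–1.5. This noise is already counted in Step 1; it is not a second loss.

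**The case against.** The strongest objection is that the documents never say baseline was left out. They are a past-tense summary that also omits SDs, prior values and stopping thresholds, and they point to a methods publication. That stands, and it is why the first request is for a statement of what was done.

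Second, analysing change is valid under randomization, so this is a choice between two valid analyses. That is true; the point concerns efficiency only.

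Third, the size is assumed and includes zero. The 35% needs equal SDs and a correlation near 0.3. The entry floor, and arguably the requirement that every patient be on high-dose vasopressors, compress the enrollment SD and favour smaller savings. This stands. Nor is 35% a mathematical ceiling: at k = 0.8 the saving would be 36–54% for ρ of 0.2–0.9.

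Fourth, the simulated gains depend on the model. With an assumed smoothing prior across doses (step SD 1), power at SD 4 rose from 0.929 to 0.931–0.948 for savings of 4–35%, a gain of 0.2 to 1.9 points. A smaller run without smoothing (1,500 trials per setting) gave larger gains at SD 4, from 90.3% to 94.5% and 95.3% at 20% and 35% saved. The direction is stable; the exact size is not.

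Fifth, the software named for the Bayesian analyses may not accept a covariate. The documents do not say. This affects how the adjusted model would be implemented, not whether it is worth having.

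**Conclusion.** The concern holds. As described, the primary SOFA model does not use a baseline value that every patient has, and in large samples it cannot gain precision from leaving it out. The variance saving is about 0–35% for k of 1.0–1.5 and ρ of 0.3–0.8, with the lower part of that range plausible because of the entry floor. The gain in the probability of a positive trial is about 0–3 points at a change SD of 3–4 and up to about 7 at SD 5, and probably less at SD 4 once doses are smoothed. These figures rest on assumed SDs, correlations and control mortality. Nothing here shows the stated 4.3% or 91.1% to be wrong, or the unadjusted analysis to be invalid. It is an improvement that should be made, held with medium confidence because the unseen publication may already contain the term.

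**What to change.** **This trial.** State whether the SOFA model contained an enrollment SOFA term. If it did not, keep the unadjusted result as primary and report the baseline-adjusted dose contrasts and posterior probabilities beside it, labelled as a sensitivity analysis.

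**A successor trial, or the design stage.** Include enrollment SOFA as a linear covariate in the dose-response model that serves both the 90% criterion and the allocation updates. Report the unadjusted change as supportive. Re-simulate type I error and power for the adjusted rule.

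**Cost.** One model term, about one degree of freedom out of up to 250 patients, and no new data. At the design stage, add a rerun of the operating-characteristic simulations and a check that the software takes a covariate. For the completed trial, the sensitivity model can be fitted in other software.

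### Dose-level tests of the secondary outcomes make no allowance for enrolment period, although dose allocation was re-weighted throughout a five-year accrual

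*Combined protocol and SAP*

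**What the plan says.** The opening section gives the accrual window: "The trial took place from January 2013 to February 2018". Under Treatment Assignment, the first 40 patients are split equally among the arms, and then "From that point on, interim analyses were conducted every 12 patients". At each of these looks, "the relative allocation probability of the three active arms were adjusted to be proportional to the probability each arm would lead to the greatest improvement", with SOFA as the measure. The same section holds control at about one-third by site-based blocks, and gives shifts in local practice as one reason for doing so.

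Assessments and Outcome Measures lists the secondary outcomes: length of stay in the ICU and in hospital, and the share of patients with withdrawal of care. The Statistical Analysis section then says "Except for these primary outcomes, remaining data were analyzed using frequentist statistics" and "Categorical data were compared using Chi-square tests, while continuous variables were compared with ANOVA or Wilcoxon rank sum based on normality", two-sided at 0.05. It describes no term for enrolment period, interim block or site in these tests. It also does not say which contrasts they address: all four arms, each dose against control, or all carnitine against control.

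**The concern.** An unstratified Chi-square, ANOVA or rank-sum test treats patients as exchangeable across arms. Here that holds only among patients who faced the same allocation probabilities. A dose that lost favour will consist mainly of early patients, and the dose that gained favour mainly of later ones.

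Length of stay and withdrawal of care depend on local practice, which can change over five years. If it does, an early-weighted dose differs from a late-weighted one even when treatment has no effect on the outcome. A reader could then take a calendar effect for a dose effect, at a false-positive rate above the nominal 5%. The plan recognises this hazard for the control comparison, and its safeguard acts on the control share. It does nothing to balance the doses against each other over time.

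**Working it through.** **Inputs from the documents.** Up to 250 patients; 40 in the burn-in; re-weighting every 12 patients; control about one-third; power scenario with SOFA effects 0, 1 and 2; test level 0.05.

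**Assumed, because not given.** All 250 enrolled with no early stopping; 10 per arm in the burn-in; SD of SOFA change 4 (3 to 5 for the power check); control mortality 30% to 50%; independent flat arm means in place of the dose-response model; linear drift; no treatment effect on the secondary outcome.

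**The plan's own figures.** At SD 4 the simulated power in the 0/1/2 scenario is 91.0% to 91.6%, against 91.1% stated; over SD 3 to 5 it is 84% to 95%. The simulated rate of a positive trial with no effect is 12% to 16%, against 4.3% stated. The smoothing prior, stopping thresholds, SD, control mortality and phase III success criterion are not given, so the 4.3% can be neither confirmed nor refuted. The plan states no error rate for the secondary tests.

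**When each arm enrolled (0 = first patient, 1 = last).** The burn-in has mean position 20/250 = 0.08. The other 210 patients have mean position (40 + 105)/250 = 0.58.
- Control: 10 + 210/3 = 80 patients, mean (10 × 0.08 + 70 × 0.58)/80 = 0.52.
- All active: 30 + 140 = 170 patients, mean (30 × 0.08 + 140 × 0.58)/170 = 0.49.
- Single doses need simulation. In the 0/1/2 scenario the means are 0.23 (low), 0.35 (medium) and 0.55 (high), with about 20, 40 and 110 patients.

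With no SOFA effect, chance still drives allocation: the smallest, middle and largest dose arms average about 27, 50 and 93 patients.

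**Expected false difference.** This is the total drift times the difference in mean position. With 1.0 SD of drift in the 0/1/2 scenario:
- low versus control: 0.52 − 0.23 = 0.29 SD
- high versus low: 0.55 − 0.23 = 0.32 SD
- high versus control: 0.55 − 0.52 = 0.03 SD
- all active versus control: 0.52 − 0.49 = 0.03 SD

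If withdrawal falls from 35% to 15%, low versus control is off by 0.29 × 20 = 5.8 percentage points. The simulated figure for the least-allocated dose is 6.2.

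**Four-arm false-positive rate at nominal 5%, unstratified.**

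| Assumed drift over accrual | No SOFA effect | SOFA 0/1/2 |
|---|---|---|
| None, stay / withdrawal | 5.0% / 4.4% | 4.9% / 5.0% |
| Stay, 0.5 SD | 6.6% | 8.2% |
| Stay, 1.0 SD | 11.9% | 20.6% |
| Withdrawal 30% to 20% | 5.0% to 5.6% | 5.8% to 6.6% |
| Withdrawal 35% to 15% | 7.2% | 9.6% |
| Withdrawal 35% to 10% | 8.2% | 13.7% |

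Most entries rest on 6,000 simulated trials (standard error near 5%: √(0.05 × 0.95/6000) = 0.3 points). The last row, and the lower value in each range, come from runs of 1,200 to 1,500 trials (about 0.6 points).

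**Pairwise tests with 1.0 SD drift (no SOFA effect, then 0/1/2).**
- Most-allocated dose versus control: 5.0%, 5.9%.
- Least-allocated dose versus control: 10.7%, 17.1%.
- Most- versus least-allocated dose: 12.1%, 21.4%.

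All carnitine versus control stays at 4.3% to 5.3% for drift up to 1.0 SD, or withdrawal falling from 40% to 10%.

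**With allowance for period.** Score and rank tests stratified by six enrolment periods reject in 4.1% to 5.6%. A linear model with enrolment-block terms gives 4.8% to 5.3% for stay and 5.3% to 6.9% for withdrawal.

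**The case against.** The strongest reply has four parts.

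- **No contrast is named.** ANOVA suggests several groups, but rank-sum is a two-group test. If the secondary analysis is only all carnitine versus control, there is little to correct. This stands: the concern applies to dose-level comparisons if they are made, and the plan does not exclude them.
- **The documents show no drift.** This also stands. Every rate above 5% depends on an assumed trend, and for modest drift the excess is at most about 3 points.
- **The 0/1/2 scenario is an awkward null.** The plan pairs those SOFA effects with mortality effects of 0, 6% and 12%, and a dose that lowers mortality by 12% would hardly leave length of stay untouched. This is fair. The no-SOFA-effect column is the cleaner error rate, and the 0/1/2 column is better read as showing how large the calendar bias can become. With strong drift the cleaner column still gives about 8% to 12%.
- **These outcomes lie outside the success rule.** True, and this limits the weight of the point.

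A reader might also infer that doses were dropped, or that only the pooled active-versus-control comparison is safe. The documents support neither. Treatment Assignment describes re-weighting without a rule for dropping an arm. The most-allocated dose enrolled at nearly the same mean time as control, so that comparison also keeps close to 5%.

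**Conclusion.** The concern holds for four-arm comparisons, for one dose against another, and for a down-weighted dose against control. In these, any calendar trend in the outcome is partly confounded with dose, and the tests as described do not remove it. The inflation is small under modest drift and material only under strong drift.

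The result rests on full accrual to 250, a linear trend and the assumed SOFA SD. That the tests pool all patients without adjustment is inferred from their names, since the plan does not say so outright.

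Three stronger readings are not supported. The first is that any drift at all invalidates the 5% level: at withdrawal falling from 30% to 20% with no SOFA effect, the rate is 5.0% to 5.6%. The second is that the reported secondary results are wrong: the documents contain no data on drift. The third is that the trial's declaration of success is affected: it rests on SOFA and predicted mortality, not on these tests.

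**What to change.** State which secondary contrasts are tested. For any four-arm or dose-specific contrast, stratify by allocation period: the burn-in as one stratum, then about five groups of successive interim blocks. With 250 patients that is 210/5 = 42 patients per group, or three to four blocks of 12. Use a Cochran-Mantel-Haenszel test for withdrawal of care and a stratified rank test for length of stay (van Elteren for two groups, stratified Kruskal-Wallis for four). Alternatively, limit secondary inference to all carnitine versus control.

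Do not cross period with site. Six periods by sixteen sites gives 96 strata for 250 patients, about 2.6 each. In one setting without drift (0/1/2 allocation, equal-sized sites, high dose lowering withdrawal from 30% to 10%), power was 91% unstratified, 90% by period and 71% by period and site. The calendar bias is removed by period alone.

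The change takes about one sentence in the Statistical Analysis section. It should need no new data, because central web-based allocation should already hold enrolment order. If there is no drift, the loss is about 2 to 3 percentage points of power (1 point in the setting above). The document is written in the past tense, so in practice this may be a stratified re-analysis reported beside the planned tests.
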